- Hospitalization for worsening PAH
- Initiation of parenteral prostanoids
- $\geq 15\%$ decline from baseline in 6MWD accompanied with continued or worsening WHO FC III or IV symptoms. The decline in 6MWD must be confirmed with a repeat test on a different day within 2 weeks. (Baseline is defined by the randomization visit in Study AV-101-002 for those on AV-101 and the Week 24 visit for those on placebo in Study AV-101-002).

Clinical Improvement from baseline will be assessed by the proportion of subjects achieving all 3 of the following components at 6 month intervals:

- WHO FC improvement or maintenance of WHO FC II status
- NT-proBNP $\geq 30\%$ improvement or < 300 pg/ml
- 6MWD ≥ 30 -meter improvement

The change from baseline in the REVEAL Lite 2.0 risk score ([Benza, 2020](#)) at 6 month intervals classified as low, intermediate, or high risk will be assessed using the following variables to derive the risk score:

- Estimated Glomerular Filtration Rate (eGFR) in ml/min/1.73 m² or renal insufficiency if GFR is unavailable
- WHO FC

- Systolic blood pressure and heart rate
- 6MWD
- NT-proBNP

Transthoracic Echocardiogram will be assessed and evaluated at 6 month intervals.

Safety and tolerability of AV-101 will be assessed using the following:

- Adverse Events
- Pulmonary Function Tests at 24-week intervals (Spirometry including FEV₁ and FVC, peripheral oxygen saturations and DLCO [Diffusing Capacity of the Lungs for Carbon Monoxide])
- Safety Laboratory Tests at Weeks 4 and 12, and at 12-week intervals thereafter (including chemistry and complete blood count)

Adverse events will be collected throughout the study period.

Safety data analyses

The independent DSMB will monitor safety at regular intervals throughout the Phase 2b/3 study as well as during the LTE study. Details regarding the members, meeting frequency and stopping rules will be specified in the DSMB charter.

Blinding and unblinding considerations

The study will remain blinded until the optimal dose from Study AV-101-002 has been identified. In the event of a medical emergency, the Investigator will be able to receive the treatment assignment, if required to provide optimal care of the subject. Instructions for Emergency Unblinding can be found in the IWRS Manual. See also [Section 7.6](#) Procedures for Breaking the Treatment Code.

Compliance

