The Week 24 end of study visit of the parent study (AV-101-002) also represents the baseline visit for the LTE study (AV-101-003). The following assessments will be conducted/collected during the baseline visit of the LTE and at selected time points specified in the Schedule of Assessments (Table 1). Additional procedures deemed necessary as part of standard of care may be performed at the discretion of the Investigator. All missed visits and any performed procedures that are not protocol-specified activities must be documented in the subject's medical record and the appropriate eCRF. General considerations for study visits include, but are not limited to the following:

- No protocol waivers or exemptions are allowed.
- Immediate safety concerns should be discussed with the CRO Medical Monitor immediately upon occurrence or awareness to determine if the subject should continue or discontinue study drug.
- Adherence to the study design requirements, including those specified in the Schedule of Assessments, is essential and required for study conduct (see Section 6.7.1 for COVID-19 considerations).
- The Investigator will obtain written informed consent before the end of study visit for study AV-101-002 and as specified in Section 9.1.3 (Informed Consent Process). Upon the subject's agreement, their primary health care provider should be informed about the subject's enrollment in the study.
- Order of Procedures:
 - Health-related QoL assessments should be performed prior to all other study procedures.
 - Vital signs should be collected prior to blood draws. Blood samples for NT-proBNP levels should be collected prior to the 6MWT.
 - All other study assessments should also be performed, according to the Schedule of Assessments (Table 1).
- **Unscheduled visits:** may occur at any time during the study with the assessments to be performed according to the Investigator's judgment. Unscheduled visits may also be necessary for study drug dispensing following temporary withdrawal as described in Sections 6.7 and 7.7.

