- 4) Levels and trends in LTE safety and effectiveness after 24 weeks of optimal dose treatment in each of the four treatment groups will be reported.

Other comparisons will be outlined in the Statistical Analysis Plan.

The association of LTE AV-101 treatment groups with levels and trends in LTE safety will be explored with a continuous AV-101 treatment exposure based on average weekly dose intensity. Planned weekly dose intensity during the parent trial ranges from zero among those who only received placebo treatment, 140 mg/week among those randomized to 10 mg per dose BID, 490 mg/week among those randomized to 35 mg per dose BID and 980 mg/week among those randomized to 70 mg per dose BID. With dose titration, early treatment discontinuation, or missed doses, average dose intensity per week will be calculated by summing up AV-101 with the cumulative sum divided by the duration of treatment in weeks.

Safety and effectiveness endpoints collected while subjects are participating in the parent study will serve as the benchmark for safety and effectiveness endpoints collected during the LTE study. LTE levels of safety and effectiveness endpoints will be presented by LTE treatment groups and LTE visits intervals disaggregated by visits prior to or after subjects are dosed with the optimal dose. These safety and effectiveness levels will be presented using descriptive statistics applicable to continuous or categorical data. Trends or patterns over time in a select set of safety and effectiveness measures will be presented graphically. Continuous data will be summarized using the following descriptive statistics: number of observations, mean, standard deviation, standard error, median, minimum, and maximum. Categorical data will be summarized using frequencies and percentages.

Changes from baseline will be calculated as the later value minus the baseline value. Baseline will be defined for specific endpoints as the time prior to starting active treatment with AV-101 in either the LTE or the parent study. Baseline values for subjects will consist of the baseline values during the parent trial among subjects in the always active treatment groups (optimal dose [Group 1] or non-optimal dose [Group 2]). For subjects who are initially assigned to placebo in the parent

trial, baseline values consist of either Week 24 parent trial values or baseline LTE prior to re-randomization to active treatment.

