8.4 Baseline and Demographics and Subject Study Disposition

With exception of the delayed-start analysis, for both the efficacy and safety analyses, baseline will be defined as the time prior to starting active treatment with AV-101 in either the LTE or the parent study. For Groups 1 and 2, since the subjects start receiving active treatment in the parent study, the baseline will be the values prior to first dose during the parent trial. For Groups 3 and 4, the subjects receive placebo in the parent trial and then receive active treatment in the LTE study, thus, the baseline will be the values prior to the first dose in LTE study.

Demographics and baseline data, medical and surgical history will be summarized using the screened analysis set. These demographics and baseline data will be presented by the LTE treatment groups as described in [Section 8.1](#).

Demographic and baseline data will be summarized using summary statistics of mean, standard deviation, median, lower quartile, upper quartile, min and max for continuous variables and number and percentage of subjects in each category.

Subject treatment status and study participation status will be reported for the safety analysis set. Subjects who completed all LTE assessments and early treatment discontinuation and withdrawal from the study including reasons for treatment or study discontinuation will be reported by LTE treatment groups.

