A Cox model will be fitted to time to clinical worsening with terms for time-varying by treatment dose groups, continuous LTE baseline REVEAL Lite 2.0 score (among those randomized to placebo in Phase 3), continuous parent baseline REVEAL Lite 2.0 score, and IPAH/HPAH or Non-IPAH/HPAH category.

The hazard ratio and its 95% CI for the pairwise treatment dose groups will be reported for:

- Always on the optimal dose (Group 1) versus always on placebo (Group 4)
- Always on the optimal dose (Group 1) versus on placebo followed by an active dose (Group 3)
- Always on the optimal dose (Group 1) versus always on a non-optimal dose (Group 2)

Kaplan-Meier curves by parent trial treatment groups will be generated.

5) Achieving multicomponent clinical improvement will be analyzed as a binary as well as a time to event response throughout the LTE period

a) Binary response throughout LTE period: At each LTE visit, a subject response is set to 1 for achieving multicomponent clinical improvement if he meets all of the following three conditions:

- FC improvement or maintenance of FC II status
- NT-proBNP \geq 30% improvement or $<$ 300 pg/ml
- 6MWD \geq 30 meters improvement

Otherwise, the response value is 0.

A logistic regression model will be fitted to the binary response of achieving multicomponent clinical improvement at each visit. The explanatory variables will include LTE treatment groups categorical visit, LTE treatment groups by visit interaction, continuous LTE baseline REVEAL Lite 2.0 score, continuous parent baseline REVEAL Lite 2.0 score, and IPAH/HPAH or Non-IPAH/HPAH category. The subject's multicomponent clinical improvement status during the parent study may be considered as an explanatory variable. Subjects will be specified as clusters.

b) **Time to Event Response from start to end of the LTE:** Time to achieve multicomponent clinical improvement response is defined as the days since the first

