dose that a subject achieves clinical improvement in all 3 components from the start through the end of LTE. The number of days between the date that a subject meets all of the multicomponent improvement parameters and the first LTE dose date is the time to achieving multicomponent improvement. A subject who does not experience multicomponent improvement is censored during the time interval. A subject who is lost to follow-up without recording this multicomponent improvement is censored at the last visit in which the above parameters are recorded. Supplemental analyses will be performed where those lost to follow-up are considered a failure at the time of the lost to follow-up.

The Cox hazard model as described for time to clinical worsening will be implemented for time to multicomponent clinical improvement.

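### Time to multicomponent improvement is counted from the first LTE dose, but Groups 1 and 2 are judged against a baseline about 24 weeks earlier, so the Group 1 v 4 and 1 v 3 hazard ratios mix prevalent with new responses

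*Combined protocol and SAP*

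**What the plan says.** - **Clock.** Section 8.5.2, item 5(b), takes the days between the date on which all three components are met and the first LTE dose: "the first LTE dose date is the time to achieving multicomponent improvement". One origin serves all four groups.
- **Yardstick.** The Synopsis defines the endpoint as a change: "Clinical Improvement from baseline will be assessed by the proportion of subjects achieving all 3 of the following components". Item 5 does not say which baseline is meant. Section 8.4 gives the general rule: "With exception of the delayed-start analysis, for both the efficacy and safety analyses, baseline will be defined as the time prior to starting active treatment". For Groups 1 and 2, "the baseline will be the values prior to first dose during the parent trial"; for Groups 3 and 4, "the baseline will be the values prior to the first dose in LTE study". Section 8.1 agrees: "Baseline values for subjects will consist of the baseline values during the parent trial among subjects in the always active treatment groups".
- **Gap.** The introduction to Section 6 makes the parent Week 24 visit the LTE baseline visit.
- **Model.** Item 5(b) borrows the Cox model from time to clinical worsening (item 4), with pairwise hazard ratios for Group 1 against Groups 4, 3 and 2. The item 4 clock starts at the first parent-trial dose, so the borrowed model comes from an analysis with a different origin.
- **Earlier response.** Item 5(a) allows parent-study improvement status as an optional covariate in the logistic model. Item 5(b) has no counterpart, and the borrowed Cox terms do not include it.

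**The concern.** Groups 1 and 2 enter the LTE with about 24 weeks of AV-101 that count towards their improvement but not towards their event time. Groups 3 and 4 start drug, baseline and clock together. A Group 1 subject who improved during the parent study and has kept the improvement is recorded as a very fast responder. In Group 4 a subject can be recorded that early only by improving within weeks of first exposure.

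The Group 1 v 4 and 1 v 3 contrasts thus set carried-over plus new responses against new responses alone. The hazard ratio could differ from 1 when the time course after starting AV-101 is the same in both groups. This is a listed endpoint in the first effectiveness tier, and the Synopsis says the summaries will support regulatory submissions.

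**Working it through.** The documents state no response rate, event count or hazard ratio for this endpoint, so there is no planned figure to reproduce.

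**1. Offset (from the documents).** Parent baseline to LTE entry is 24 × 7 = 168 days. Table 1 schedules WHO FC, NT-proBNP and 6MWT at LTE Week 4, about 28 days after the first LTE dose. A Group 1 subject recorded there has had 168 + 28 = 196 days of AV-101; a Group 4 subject has had 28.

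**2. Assumptions (not in the documents).** Both groups share one response curve from the first AV-101 dose, so the true hazard ratio is 1. The curve is set by response at 24 and 72 weeks, p24/p72: 20/40%, 15/30% or 30/50%. The hazard is constant within each segment. LTE follow-up is 48 weeks. A fraction r of parent-study responders still responds in the LTE, and lost responders do not respond again.

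**3. Hand check for 20/40%.**
- λ1 = −ln(0.80)/24 = 0.0093 per week; λ2 = −ln(0.60/0.80)/48 = 0.0060 per week.
- LTE Week 4, r = 1: Group 1 is 1 − 0.80·exp(−4λ2) = 22%; Group 4 is 1 − exp(−4λ1) = 4%.
- LTE Week 48: Group 4 is 1 − 0.80·exp(−24λ2) = 30.7%. Group 1 is 0.20r + 0.20.

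| r | Group 1 at LTE Week 48 | ln(1 − Group 1) / ln(1 − Group 4) |
|---|---|---|
| 100% | 40% | 0.511/0.367 = 1.39 |
| 70% | 34% | 0.416/0.367 = 1.13 |
| 50% | 30% | 0.357/0.367 = 0.97 |

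The last column is a crude Week 48 ratio of cumulative hazards. The Cox estimate also reflects when the events fall, so it differs somewhat.

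**4. Cox hazard ratio, Group 1 v 4, simulated on the LTE visit schedule over all three curves.**

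| Persistence | Hazard ratio (true value 1.0) |
|---|---|
| 100% | about 1.4-1.5 |
| 70% | about 1.1-1.2 |
| 50% | about 0.9-1.0 |

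**5. Other assumptions.**
- Front-loaded response (17% by Week 12, 20% by Week 24, 25% by Week 72): 1.22, 0.88 and 0.66 at 100%, 70% and 50% persistence.
- Constant hazard, 10-40% response by Week 24, 96 LTE weeks, lost responders able to respond again: 1.31-1.61 at full persistence and 1.21-1.39 at 70%.
- Scoring only every 24 weeks: about 1.35-1.41 at full persistence and 1.01-1.14 at 70%.

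**6. After realignment.** With the clock started at the first AV-101 dose, the hazard ratio is 0.97-1.02 for the three curves and 1.00-1.01 under the constant hazard.

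**7. Keeping the LTE clock and dropping earlier responders.** Under a constant hazard this also gives 1.00-1.01. Under a falling hazard it does not. For 20/40%, the remaining Group 1 subjects are at λ2 during LTE Weeks 0-24 while Group 4 is at λ1, a ratio of 0.0060/0.0093 ≈ 0.64; afterwards the ratio is 1. The overall estimate therefore falls below 1. This approach can support a sensitivity analysis but cannot replace realignment.

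**The case against.** **The baseline is inferred.** Item 5 is silent. Item 2 of the same section and the Tier 2 endpoints in Section 8.5.3 use change from LTE baseline, and Section 6.1 says only that parent values may be used, depending on the outcome. If LTE baseline was meant, most carried-over responses disappear. This stands as a reason to name the baseline. It does not displace the reading used here, because Section 8.4 exempts only the delayed-start analysis. The alternative has its own fault: Groups 1 and 2 would need a further 30 m gain on values already improved by treatment.

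**The direction is not fixed.** A reader might infer that every parent-study responder scores at the first LTE visit, and that the hazard ratio must favour Group 1. The documents support neither. An event requires all three components to be met during the LTE, so a lapsed responder does not score, and no persistence rate is given. With enough loss of response the bias vanishes or reverses.

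**Scoring visits are inconsistent.** Item 5(a) scores every LTE visit; the Synopsis and Sections 2.2 and 6.6.6 refer to 6-month intervals. Under the latter, the 22% v 4% contrast at Week 4 would not be seen, but the distortion under full persistence remains.

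**It may capture early-start benefit.** Section 8.5.1 addresses that separately, at matched study weeks. Item 5(b) combines two baselines with one LTE clock and measures neither early-start benefit nor speed of response.

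**Weight.** The study's objective is long-term safety, and this is one of many effectiveness analyses with no power claim. That limits the consequence but does not make the hazard ratio interpretable. The Section 8.1 reporting after 24 weeks of optimal dose does not repair this Cox model.

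**Conclusion.** The concern holds for Group 1 v 4 and Group 1 v 3. Read with Section 8.4, item 5(b) starts the clock about 24 weeks after the baseline against which Groups 1 and 2 are judged, and nothing in it removes or adjusts for subjects already responding. Those hazard ratios mix prevalence with incidence. Group 1 v 2 shares clock and baseline and is not affected by this mismatch.

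The mismatch comes from the text; its size does not. For the three main curves, the apparent hazard ratio when the truth is 1.0 runs from about 1.4-1.5 (all responses persist) to about 0.9-1.0 (half persist, with no second response). Bias towards Group 1 is to be expected when most responses persist, but that is conditional. The conclusion also rests on the Section 8.4 baseline applying to item 5.

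**What to change.** 1. In item 5, name the baseline as the last value before the first AV-101 dose, consistent with Section 8.4.
2. In item 5(b), start the clock at the first AV-101 dose: the parent first dose for Groups 1 and 2, the LTE first dose for Groups 3 and 4. Include parent-study visits for Groups 1 and 2, and state which visits are scored.
3. As a sensitivity analysis, keep the LTE clock but exclude from the risk set anyone who met all three components during the parent study or at LTE entry. Note that this can understate Group 1 if response slows with time on drug.
4. State as a limitation that Groups 1 and 2 are selected for having completed 24 weeks on AV-101 (Section 4.1), whereas Groups 3 and 4 can drop out from their first AV-101 dose. Equal time on drug is therefore still not a fully like-for-like comparison.

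Cost: SAP wording, linkage to parent visit data and a little more analysis. No new assessments are needed.

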1.1 Background

Data from the REVEAL registry demonstrate that, from the time of diagnostic right heart catheterization and even with treatment, patients with PAH had 1-, 3-, 5-, and 7-year survival rates of 85%, 68%, 57%, and 49%, respectively (McGoon and Miller, 2012). This reflects the serious nature of the disease and the need for alternative PAH treatments with new mechanisms of action that directly target the proliferative nature of the vasculopathy, with the ultimate goal being to halt or reverse disease progression.

Clinical efficacy of oral imatinib mesylate in the treatment of PAH was observed in Functional Class II-IV patients in the Phase 3 IMPRES trial, in which the primary endpoint, six minute walk distance (6MWD), as well as secondary endpoints measuring pulmonary vascular resistance (PVR), mean pulmonary arterial pressure (mPAP), cardiac output (CO), and N-Terminal Prohormone-B Natriuretic Peptide (NT-proBNP) all showed statistically significant and therapeutically relevant improvements on top of the maximal standard of care (Hoepfer et al., 2013). However, oral imatinib was not well tolerated and further clinical development was halted.

At therapeutic concentrations, imatinib is an inhibitor of the Abelson murine leukemia viral oncogene homolog (ABL), Colony Stimulating Factor 1 Receptor (CSF1R), KIT Proto-Oncogene Receptor Tyrosine Kinase (cKIT), Discoidin Domain Receptor (DDR), Lymphocyte-Specific Protein Tyrosine Kinase (LCK) and Platelet-derived growth factor receptor (PDGFR) kinases (Davis et al., 2011). Signaling through each of these kinases has been implicated in histopathologic remodeling in PAH including PDGFR mediated proliferation and apoptotic resistance of vascular smooth muscle and endothelial cells, KIT expression directly in the vasculature and its influence on precursor cells, fibrotic signaling and recovery mediated by DDR and ABL, as well as immune dysregulation via LCK, CSF1R and KIT (Schermuly et al., 2005; Montani 2011; Rojo et al., 2019; Leitinger et al., 2014; and Rossy et al., 2012). Due to its anti-proliferative effects, imatinib has the potential to be a disease-modifying therapy for PAH.

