Trends or patterns over time in safety and effectiveness measures will be presented using repeated measures data analysis methods applicable to categorical or continuous data. Time-to-event analyses will be performed using Cox models with time-independent and time-varying covariates, specifically, extent of AV-101 dose intensity as continuous or categorical variables. For time to event data like overall survival, the starting period is the day prior to the first dose in the parent trial. Kaplan-Meier procedures for time -to-event analysis will also be performed.

For longitudinal continuous variables, the shape of the effectiveness trajectory (trends), repeated measures models over time will be fitted to assess whether the effectiveness measure indicates waxing, waning or remaining persistently over time. During the LTE, visits may be grouped into before or after optimal dose is administered. Levels of the LTE effectiveness endpoints before or after optimal dose treatment during the LTE will be reported.

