Visits within a subject form a cluster. Estimated proportions by treatment group and visit will be reported. For Week 24 after optimal dose treatment, the log of odds and proportions of subjects who maintain or improve WHO FC and their 95%CI will be reported by treatment groups. Odd ratios (OR) and 95%CI for subjects always on optimal dose (Group 1) relative to those subjects on always on placebo (Group 4) will be reported. OR and 95%CI among subjects always on optimal dose (Group 1) relative to those of subjects on placebo and then active treatment (Group 3) and OR and 95%CI among subjects always on optimal dose (Group 1) relative to those of subjects on non-optimal dose (Group 2) will also be reported.

4) Time to Clinical Worsening

Time to clinical worsening while in the parent trial and LTE will be based on the first occurrence of any of the following events for each subject.

- Death
- Initiation of parenteral prostanoids
- Hospitalization for worsening PAH
- $\geq 15\%$ decline from baseline in 6MWD and accompanied with progression to or continued WHO FC III or IV symptoms

A subject is evaluated for experiencing any of the above components of clinical worsening throughout the parent trial and LTE study period. Time to clinical worsening is the number of days between the earliest occurrence of the clinical worsening component and the date of the first dose in the parent trial. With treatment groups that change over time intervals, event and censoring will be defined within each time interval. A subject who does not experience any of the clinical worsening component throughout a treatment period/interval is censored and is assigned time to worsening status by the end of the interval. Subjects who are lost to follow-up are typically considered censored. Supplemental analyses will be performed where subjects with an unknown clinical worsening event will be considered to

experience the event and the time to clinical worsening status is the last contact with the subject.

The probability of clinical worsening every 24 weeks after the first dose in the parent trial throughout the LTE will be reported, descriptively as well as based on a Cox model for time to clinical worsening while holding covariates at their means.

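### Time to multicomponent improvement has no rule for death, so a Kaplan-Meier or Cox-based probability of improvement that censors deaths would overstate the share of subjects who improve

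*Combined protocol and SAP*

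**What the plan says.** Time to achieving multicomponent improvement is a listed endpoint (section 2.2) and belongs to the first tier of effectiveness analyses (section 8.5.2, item 5). Item 5(b) counts days from the first LTE dose and gives these rules:

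- Subjects without the event: "A subject who does not experience multicomponent improvement is censored during the time interval".
- Subjects lost to follow-up without the event: each "is censored at the last visit in which the above parameters are recorded".
- A supplement for the same subjects: "Supplemental analyses will be performed where those lost to follow-up are considered a failure at the time of the lost to follow-up".
- The model: "The Cox hazard model as described for time to clinical worsening will be implemented for time to multicomponent clinical improvement".

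Death is not mentioned in item 5(b). Section 6.8.1 lists subjects who died apart from those lost to follow-up, so the loss-to-follow-up rule does not cover deaths. Section 6.8.2 treats a death as withdrawal from the study.

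On probabilities, section 8.1 says in general: "Kaplan-Meier procedures for time -to-event analysis will also be performed". The synopsis says much the same. Item 4, on clinical worsening, adds: "The probability of clinical worsening every 24 weeks after the first dose in the parent trial throughout the LTE will be reported", both descriptively and "based on a Cox model for time to clinical worsening while holding covariates at their means". No cumulative-incidence or competing-risk method is named for improvement.

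**The concern.** A subject who dies unimproved can no longer improve. Censoring that subject at death assumes that improvement could still have followed at the same rate as in the survivors. One minus Kaplan-Meier, or one minus a Cox survival curve, then estimates the chance of improvement with death abolished.

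For clinical worsening the question does not arise, because death is a component of the event. The difficulty appears when the same machinery is used for a favourable event. Elsewhere the plan does provide for death: section 8.5.1 imputes a poor 6MWD change for subjects who died. The gap is therefore specific to this endpoint.

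At stake is any stated probability of improvement, and any visual comparison of improvement curves between LTE groups. Two groups with the same improvement rate among the living but different mortality would show the same curve, although fewer subjects improve where more die.

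**Working it through.** The plan states no improvement probability, event count or power for this endpoint, so there is no figure to reproduce. The check is how far the two estimands differ under stated assumptions.

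**Inputs**

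- Death hazard from the documents: section 1.1 cites registry "1-, 3-, 5-, and 7-year survival rates of 85%, 68%, 57%, and 49%, respectively". This gives -ln(0.85) = 0.163 per year over the first year and -ln(0.68)/3 = 0.129 per year over three years. The three-year figure, rounded to 0.13, serves as an upper reference.
- Death hazard for LTE entrants: not given. Assumed 0.03, 0.05 and 0.08 per year, because entrants have completed 24 weeks in the parent study.
- Improvement hazard: not given. Assumed 0.2 and 0.4 per year, constant.

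**Formulas**, with improvement hazard *a*, death hazard *d* and time *T*

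- One minus Kaplan-Meier with deaths censored: 1 - exp(-aT).
- Share who improve (cumulative incidence): a/(a+d) × [1 - exp(-(a+d)T)].

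Example, a = 0.4, d = 0.08, T = 2: the first is 1 - exp(-0.8) = 55.1%. The second is 0.4/0.48 × [1 - exp(-0.96)] = 0.833 × 0.617 = 51.4%. The difference is 3.6 points (differences are taken before rounding).

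**Results at 2 years**

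| Improvement hazard | Death hazard | 1 - KM | Cumulative incidence | Overstatement (points) |
|---|---|---|---|---|
| 0.2 | 0.03 | 33.0% | 32.1% | 0.9 |
| 0.2 | 0.05 | 33.0% | 31.5% | 1.5 |
| 0.2 | 0.08 | 33.0% | 30.6% | 2.3 |
| 0.2 | 0.13 | 33.0% | 29.3% | 3.7 |
| 0.4 | 0.03 | 55.1% | 53.7% | 1.4 |
| 0.4 | 0.05 | 55.1% | 52.7% | 2.3 |
| 0.4 | 0.08 | 55.1% | 51.4% | 3.6 |
| 0.4 | 0.13 | 55.1% | 49.3% | 5.7 |

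For death hazards of 0.03 to 0.08, the overstatement is 0.3 to 1.2 points at 1 year and 1.8 to 6.3 points at 3 years. At 0.13 the 3-year figures are 7.0 and 9.8 points.

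**Between groups.** Take two groups with improvement hazard 0.4 and death hazards 0.03 and 0.08. Both show 55.1% at 2 years by one minus Kaplan-Meier, but the shares who improve are 53.7% and 51.4%. The cause-specific hazard ratio is 1, which is correct for the rate among subjects alive and unimproved; it does not show the 2.2-point difference in the share who improve.

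**Role of the censoring time.** A simulation (200,000 subjects per scenario, 2-year horizon, 30% improving at 1 year without deaths) compared two treatments of death. Censoring at death gave 51.2% and 50.9% for death hazards of 0.05 and 0.1625. Keeping deaths in the risk set to the end of follow-up gave 49.0% and 44.3%, in line with the cumulative incidences of 48.8% and 44.4%. The bias therefore depends on when a death leaves the risk set, which item 5(b) does not settle.

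**The case against.** The strongest reply is that the faulty output is inferred. A reader might take the plan to promise a probability of improvement. Item 5(b) contains no such sentence: the 24-week probabilities and the Kaplan-Meier curves in item 4 concern clinical worsening, which is timed from the first parent-study dose, and item 5(b) adopts the Cox model. This stands. What remains is the general Kaplan-Meier commitment in section 8.1 and the synopsis, which covers a time-to-event endpoint without exception.

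A reader might also infer that the Cox comparison is biased by deaths. It is not. With deaths censored it estimates a cause-specific hazard ratio and needs only that label.

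Nor do the documents say outright that deaths are censored when they occur. Item 5(b) does not name death, its timing phrase is loose, and section 8 leaves details to an SAP. This too stands, and it is a reason to write the rule down.

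On size, the registry rates run from diagnostic catheterization and do not describe subjects who completed the parent study and passed the investigator's exclusions. If improvement comes early (assumed 0.4 in year 1, then 0.1), the 2-year error at death hazards 0.05 and 0.08 falls to 1.2 and 1.9 points. A binomial standard error with all 370 expected subjects followed for 2 years is about 2.6 points (√(0.514 × 0.486/370)). With follow-up assumed uniform over 0 to 3 years, given staggered entry and a fixed stop on 31 December 2025, it is about 3.6 points.

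Finally, the study's objective is long-term safety, survival is reported separately, and no decision rule rests on this endpoint.

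**Conclusion.** The point holds, conditionally. As written, a subject who dies unimproved falls under the catch-all censoring rule. If the censoring takes place at death, any Kaplan-Meier or Cox-based probability of improvement is too high whenever some subjects die unimproved, and more so in a group with higher mortality.

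At assumed death hazards of 0.03 to 0.08 per year and improvement hazards of 0.2 to 0.4, the overstatement is about 1 to 4 points at 2 years. About 6 points needs the registry's three-year death rate together with the higher improvement hazard. Errors are larger at 3 years, but fewer subjects will be followed that long. All of these figures rest on constant hazards and on rates that the documents do not supply.

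A reader might infer that the curves will favour a particular LTE group or reverse a ranking. A reversal can be constructed by giving one group 0.1625 deaths per year and the other 0.05, but the documents give no mortality by group, so neither inference is supported.

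**What to change.** In section 8.5.2, item 5(b), and in the SAP:

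- State that death before improvement is a competing event, recorded at the date of death.
- Wherever a probability or curve of improvement is shown, report the Aalen-Johansen cumulative incidence by LTE group in place of one minus Kaplan-Meier or a Cox-based probability.
- Keep the Cox hazard ratio and label it cause-specific, with a note that it does not measure a difference in the chance of improving.

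A Fine-Gray model is optional. There is no need to treat discontinuation of study drug as a further competing event; that is a different question.

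The cost is a few sentences and standard software, with no new data. The reported probability of improvement becomes slightly lower.
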